Exclusion Criteria

- 1) Unwilling to use research cigarettes as part of the study
- 2) Self-reported ~~binge drinking of alcohol ($\geq 4/5$ drinks within a 2 hour period for female/male participants respectively) or use of illicit or non-prescribed drugs (excluding marijuana) ≥ 10 days in the past 30 days~~ daily use of alcohol
 - a. We will ask about daily alcohol and drug use in the phone screen, and we will use the Timeline Follow-Back to assess current and recent marijuana and alcohol use.
- 3) Currently seeking treatment to quit smoking, and/or intending to quit smoking for good in the next 30 days
 - a. This information corresponds to questions 2 & 3 of the Stages of Change measure which will be administered at the in-person screening.
 - b. These participants will be excluded, and provided with referral information for cessation services in the community.
- 4) Suicidal ideation in the past month or any past-year suicide attempts
 - a. Suicidal ideation determined by the MINI suicide subscale at the in-person screening (Questions 4 and 5)
 - b. Suicide attempt in the past year determined by MINI question 6.a. (If participant has a lifetime history of suicide attempt between 1 and 10 years ago, licensed medical monitor approval required)
 - c. If a participant indicates that he/she currently has suicidal ideation during this or any future session, the Emergency Protocol will be followed in which a Licensed Clinician will be contacted immediately, and participants will speak with the clinician over the phone and the clinician will determine the appropriate action to take to keep the child safe.
- 5) Pregnant or breastfeeding
 - a. Determined by urine test at in-person screening; tested again at each in-person visit; participant will be excluded or withdrawn if test indicates pregnancy
 - b. Self-reports current breastfeeding at in-person screening
- 6) Any medical or psychiatric conditions in which participation is likely to pose a significant threat to health or for which the condition could interfere with the ability of the participant to fully participate (as determined by LMP).
- 7) Having participated in another research study during the past year in which they were switched to research cigarettes for longer than one week.

Initial eligibility determination will be made by the RA based on the above criteria. If the participant is deemed initially eligible, the BL1 session will immediately begin. Eligibility

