- a. **Background/Descriptive Measures:** A modified version of the **PATH Demographics and Tobacco Use History** (Adolescent version) will be used to assess participant characteristics and lifetime history of tobacco product use (using a comprehensive list of combusted and non-combusted products), including ages of initiation and progression through smoking milestones such as daily use. [The Vaping History Questionnaire will be used to assess lifetime use of e-cigarettes, including e-cigarette characteristics.](#) **Social and Environmental Influences** (tobacco use by parents and peers; perceived norms for cigarettes and e-cigs) will be assessed using a modified Interpersonal Influences Questionnaire ([name] et al., 2005). We will use the reliable and valid **Smoking Stage of Change** (Velicer, Hughes, Fava, Prochaska, & DiClemente, 1995) to assess readiness to change at baseline and week 4. The **Center for Epidemiological Studies-Depression Scale** (CES-D; Radloff, 1991) is a widely used and validated 20-item questionnaire assessing depressive symptoms in the past week. This measure will be used for sample description given the high co-occurrence of smoking and depression. Respiratory symptoms will be assessed using the **American Thoracic Society Questionnaire** (ATSQ; Comstock, Tockman, Helsing, & Hennesy, 1979). Participants report the frequency of experiencing each of 8 respiratory symptoms (e.g., morning cough, wheezing, shortness of breath when walking). We recently validated this scale for assessing the severity of respiratory symptoms associated with smoking in adolescents ([name], Roberts & [name], 2015). **Nicotine Dependence** will be assessed using the modified Fagerstrom Tolerance Questionnaire (Heatherton, Kozlowski, Frecker, & Fagerström, 1991). Scores on this measure will be evaluated as an outcome at Week 4 as an index of changes in dependence as a function of VLNC exposure.

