- b. **Safety:** Pregnancy tests will be performed for all female participants at Screening/BL1, BL2, and both lab visits (weeks 2 and 4). The **suicide subscale** from the Mini International Neuropsychiatric Interview (MINI; Sheehan et al., 2010) will be used at Screening to evaluate suicide risk. CO level will be obtained at every session to evaluate level of exposure to smoke; a large increase in CO (i.e., CO > 80 ppm) can be a reason for withdrawing a participant from the study. **Brief Medical History** (Screening/BL1) assesses physical and emotional health to establish eligibility for participation (determined by the medical monitors). In subsequent sessions, the **Health Changes Questionnaire** asks whether the participant experienced any changes in his/her physical or emotional health since their last visit, including whether they have visited the doctor, the hospital, or whether they have had a change in any of their medications. Any endorsement of a negative health change will be tracked as an adverse event.
- c. **Frequency of tobacco and other drug use measures:** Past 30-day tobacco product use will be comprehensively assessed using a **Timeline Follow-Back (TLFB)**, a reliable calendar-assisted interview validated for estimating daily use of tobacco and other substances in adolescents (Lewis-Esquerre et al., 2005). The TLFB will determine: # cigarettes per day; frequency of e-cig use (including nicotine concentration in e-liquid) and use of all other tobacco products; use of alcohol (# standard drinks/day); and frequency of marijuana use and other illicit or recreational drug use. The TLFB will also be used to assess tobacco, alcohol, marijuana and other drug use between sessions to evaluate use over the course of the study.
- d. **Biomarkers. Expired breath CO** level is a reliable and valid assessment of recent smoking and will be measured using a Vitalograph CO Monitor. CO will be assessed at BL to confirm

Impact of nicotine reduction on adolescent cigarette use, alternative tobacco use, and harm from tobacco

PIs: [name] & [name]

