- g. Compensatory smoking: The possibility exists that use of VLNC cigarettes over an extended period may lead to compensatory smoking (i.e., more intense or frequent smoking in an attempt to derive more nicotine from study cigarettes). However, research to date indicates that this outcome is unlikely. We will monitor the participant's weekly cigarette use and CO levels to evaluate the extent to which compensatory smoking is occurring, and will make changes to the protocol to reduce this as necessary.
- h. Lower perceived risk of harm: The possibility exists that use of VLNC cigarettes over an extended period may lead to perceiving a reduced risk associated with VLNC cigarettes; we will debrief the participant post-study on risks associated with smoking. All cigarettes are harmful to a person's health. Smoking can lead to severe or fatal medical problems including heart disease, respiratory (breathing) problems and diseases, cancer, diabetes, and other health risks. The study cigarettes do not provide less risk than the participant's usual brand cigarette.

15. Adverse Events

a. Collection and reporting of AEs and SAEs

While participating in the trial, adverse events and changes in medications will be assessed at every study visit and carbon monoxide will be obtained. Medical events will typically be

Impact of nicotine reduction on adolescent cigarette use, alternative tobacco use, and harm from tobacco

PIs: [name] & [name]

identified during the administration of the Health Changes Questionnaire. Other events may be identified by spontaneous reports during non-scheduled assessments.

b. Questionnaire items that will be reviewed:

Health Changes Questionnaire

1) Have you noticed that your physical health or mental health have gotten worse since your last visit? If Yes, please describe.

2) Have you had any changes in medication since your last visit? If Yes, please describe:

3) Since your last visit, have you gone to the doctor? If Yes, please describe:

4) Since your last visit, have you gone to the hospital? If Yes, please describe:

No new AE required if one or more conditions below are met and the description does not otherwise meet the definition of an AE.

- 1) Existing AE already open for reported symptom
- 2) Pre-existing condition without increase in severity or frequency of symptoms (brief medical history will be updated if not previously reported).
- 3) Received preventative or follow-up medical care.
- 4) Other (explain).

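### After Screening no listed item asks about suicidal ideation, and no same-session probe is stated when a participant reports worse mental health

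*Protocol*

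**What the plan says.** The commitment is in Protocol section 4, Exclusion Criteria, item 4c: "If a participant indicates that he/she currently has suicidal ideation during this or any future session, the Emergency Protocol will be followed". A licensed clinician is then contacted immediately and decides what to do.

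The ideation items appear once. Item 4a ties ideation to MINI Questions 4 and 5 at in-person screening. Section 11.b (Safety) says the MINI suicide subscale "will be used at Screening to evaluate suicide risk", and Table 1 shows one mark for it.

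At BL2 and Weeks 1 to 4 (sections 6.b, 7.b, 8.b, 9.b and 10.b) the safety instrument is the Health Changes Questionnaire. Its item 1, in section 15.b, reads: "Have you noticed that your physical health or mental health have gotten worse since your last visit? If Yes, please describe". The other three items cover medication changes, doctor visits and hospital visits.

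Under section 11.b, reported deterioration is recorded as an adverse event (AE). Under section 15.c the medical monitor reviews every AE, the monitor or an investigator may discontinue a participant for safety, and AEs are followed until they settle. The 30-day call (sections 3 and 12) covers tobacco use and general safety.

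**The concern.** Item 4c assumes that ideation may come to light after Screening, but no later visit lists a question that asks about it. Suppose a participant answers yes to item 1 and says only that they have been feeling low. That produces an AE record. Nothing in the supplied pages tells the research assistant to ask, before the participant leaves, whether suicidal thoughts are present. The immediate response in 4c could therefore be delayed until the monitor reviews the AE, and no timing is given for that review.

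The participants are 15 to 20 years old and some are minors. Some residual risk is accepted on entry: "If participant has a lifetime history of suicide attempt between 1 and 10 years ago, licensed medical monitor approval required". The Protocol also says of the CES-D: "This measure will be used for sample description given the high co-occurrence of smoking and depression". Section 14.e lists depressed mood among possible withdrawal symptoms. The stated rules specific to suicide act either before entry (past-month ideation or a past-year attempt excludes) or after an event (an attempt or psychiatric hospitalization leads to withdrawal, section 15).

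**Working it through.** The plan gives no figure on this point, so the check is a reading of each contact, followed by the cost arithmetic.

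| Contact | Ideation item listed | General health question |
|---|---|---|
| Screening/BL1 | MINI Questions 4 and 5 | not counted |
| BL2 | none | yes (6.b) |
| Week 1 | none | yes (7.b) |
| Week 2 | none | yes (8.b) |
| Week 3 | none | yes (9.b) |
| Week 4 | none | yes (10.b) |
| 30-day call | none stated | general safety only (12) |

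An ideation item is listed at 1 of 7 contacts and at 0 of the 6 after Screening/BL1. The general question is listed at 5 of those 6. Four of the 6 (Weeks 1 to 4) fall within or at the end of the 28 days on take-home study cigarettes. The timing of the Health Changes Questionnaire is taken from the session texts, because its Table 1 row appears shifted in the PDF reading.

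Other post-Screening data that touch on mood:

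- The CES-D has one mark in Table 1 and is used for sample description.
- The MNWS and PANAS at BL2 and Week 2 measure withdrawal and affect. No alert is attached to either.
- The EMA random-prompt and tobacco-use reports ask about feeling depressed, but no threshold or link to 4c is stated. In Weeks 2 and 3 only the morning report is required (6.g), and it has no mood item.

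Cost at the planned N = 120. Minutes and rates are assumptions.

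- Minimum fix: 5 sessions × 120 = 600 administrations, plus 120 calls = 720. At 5 to 20% endorsed for mental health: 36 to 144 probes. At 3 minutes each: 108 to 432 minutes = 1.8 to 7.2 staff-hours.
- Preferred fix, lab visits: 3 visits (BL2, Weeks 2 and 4) × 120 × 1 to 3 minutes = 360 to 1,080 minutes = 6 to 18 hours.
- Preferred fix, remaining probes: Weeks 1 and 3 plus the call, 3 × 120 = 360. At 5 to 20%: 18 to 72 probes. At 3 minutes: 54 to 216 minutes = 0.9 to 3.6 hours.
- Preferred total: 6.9 to 21.6 hours.
- Clinician time: 120 × 1 to 5% = 1.2 to 6 calls × 0.5 hours = 0.6 to 3 hours.

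**The case against.** The strongest reply is that the Protocol does have a route. Item 1 names mental health, invites a description, and is asked at every session from BL2 on. A participant who describes ideation there has indicated it, and 4c applies. One who reports only worse mental health still generates an AE that a medical monitor reviews and follows, and the monitor may uncover ideation that was not mentioned. This stands. A reader might infer that ideation reaches a clinician only if it is volunteered, but sections 11.b and 15.c do not support that. What they leave open is when the review happens and whether anyone asks about ideation. Section 15.b also lets some endorsements pass without a new AE, for instance where one is already open for the symptom, although an open AE is still followed.

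Second, the Emergency Protocol that 4c invokes is not supplied, and a probe rule could well sit there or in the call script. This also stands. The finding is that no rule is stated in these pages, not that none exists.

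Third, entry screening is strict, older attempts need monitor approval, and section 14.e calls withdrawal symptoms usually mild and notes that other nicotine products are allowed. This keeps the expected event rate low but does not supply the missing question.

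Fourth, the trial looks complete. The SAP is written in the past tense, as are the Protocol's notes on virtual check-ins. The practical value may lie in any remaining visits and in reuse of this protocol.

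**Conclusion.** The point holds as a gap in the speed and specificity of detection. No ideation item is listed at the 6 contacts after Screening/BL1, and neither a same-session probe nor a review time is stated in the supplied pages. That reading of the pages is firm. Whether the gap existed in practice is less certain, because the Emergency Protocol and call script cannot be seen.

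Three stronger readings should be resisted:

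- Item 4c does not contradict the visit schedule. It says what to do once ideation is indicated, and the Health Changes Questionnaire gives an opening to indicate it.
- The pregnancy rule, "tested again at each in-person visit; participant will be excluded or withdrawn if test indicates pregnancy", does not show inconsistency. Pregnancy has an objective test and mandates withdrawal, whereas ideation is not a listed withdrawal criterion.
- The documents do not name suicidality as a risk of very low nicotine cigarettes.

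No event rate is given. The probability is expected to be low and the consequence serious. No endpoint, sample size or analysis is affected. A cheap improvement is warranted.

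**What to change.** Minimum: state that whenever Health Changes item 1 is endorsed for mental health at BL2 or Weeks 1 to 4, the research assistant asks MINI Questions 4 and 5 verbally, in private and in the same session. Do the same in the 30-day call if worse mental health is reported. If the Emergency Protocol already requires this, a cross-reference in the visit procedures is enough.

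Preferred: also list the two questions in Table 1 at BL2 (before the study cigarette is smoked), Week 2 and Week 4.

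Ask about the time since the last visit, then whether the thoughts are current, and state an action for each answer. Current ideation triggers 4c. Ideation since the last visit that is no longer current goes to the medical monitor before any further study cigarettes are dispensed.

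The change uses existing items, staff, contacts and clinician cover, plus an edit to Table 1 and the procedures through the IRB. Staff time is about 1.8 to 7.2 hours for the minimum or 6.9 to 21.6 hours for the preferred version, with 0.6 to 3 clinician hours. These totals use the planned 120; the SAP says fewer took part, so the actual cost would be lower. The downsides are a few minutes per probe, occasional extra clinician calls, and the need for privacy at community or virtual check-ins, especially for minors.

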- d. **Product Compliance and Accountability:** Participants will be required to keep track of all the cigarettes provided to them. Each week, they will return all unused cigarettes and empty or unopened cigarette packs to the research staff, and will receive incentives for doing so. Participants will be asked if they have decided to quit smoking at each lab visit. If they wish to quit, they will be asked if they still want to receive study cigarettes. If not, no cigarettes will be dispensed. The participant will be retained in the study with no penalty and will continue to complete all subsequent EMA and other self-report assessments. In an ongoing study (IRB#1404001032), we dispense research cigarettes in this manner to 15-19-year-old daily smokers with approvals from the FDA, Brown University IRB and permission (waiver) from the Rhode Island Attorney General (K01CA189300, PI [name]). We are in the process of obtaining such a waiver for the current study as well. We will provide incentives for study cigarette accountability, which we have found to increase study cigarette compliance in our prior trials. The incentive will be a payment at each in-person session, which encourages participants to keep track of their study cigarettes, minimizes hoarding of study cigarettes, and discourages sharing of study cigarettes with other people. The payment schedule for returning unsmoked cigarettes is as follows: 50-74% returned, \$5; 25-49% returned, \$2.50; and 0-24% returned, \$0. Returned empty packs will receive \$1. At each session, participants will be reminded that if they do not like their study cigarettes, they can use alternative products that are not cigarettes, as the goal of the study is to model a scenario in which a nicotine reduction policy applies only to cigarettes. Honest reporting will be encouraged throughout the study. The total possible incentive for cigarette/empty pack return is \$5.
- e. **Randomization:** Using procedures similar to our current study, a double-blind randomization procedure will be used. We will stratify on the following four variables to optimally balance conditions on factors that might influence responses to study cigarettes:
 - a) Gender
 - b) Average cigarettes per day in past month (CPD; < 8 cigarettes vs. > 8 cigarettes)
 - c) frequency of past-month alternative combustible tobacco product use (< 10 days vs. > 10 days).
 - d) frequency of past-month non-combustible tobacco product use (< 10 days vs. > 10 days).

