Cover page for Data Analysis Plan

NCT03860077

Grant number: R01DA047356

Grant Title: Impact of Nicotine Reduction on Adolescent Cigarette Use, Alternative Tobacco Use, and
Harm From Tobacco

Document date: 9/1/23

Data Analytic Approach and Power.

Overview and justification. Mixed effects models evaluated change in total cigarette use, alternative tobacco product use, study cigarette use, and biomarkers of nicotine exposure from baseline to the final study week. All analyses were with SAS V9.4 software (SAS Institute Inc., Cary, NC, USA, 2016). Due to data-collection disruptions related to the COVID-19 pandemic and intermittent data-collection challenges with the ecological momentary assessment (EMA) program, we elected to utilize the most complete data stream for primary analyses, which was Time Line Follow Back (TLFB) of outcomes collected at Week 4 and Baseline. Consistent with our prior work (e.g., ¹), aggregated timeline follow-back (TLFB) data from the final week of study cigarette use (i.e., Week 4) was compared to a one-week baseline period during which participants used usual brand cigarettes (i.e., Baseline). The mixed effect model using TLFB data was chosen over other possible analytic approaches (e.g., ANCOVA with baseline outcome covariates) to reduce bias stemming from (1) pre-randomization group differences in baseline outcome levels, and (2) missing outcome data.

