Analyses to address project aims. To address primary aims, 2-group (VLNC & NNC) x 2 repeated measures (Baseline & Week 4) mixed effects models tested the effect of the randomization group (VLNC vs. NNC) on change in cigarette use and alternative tobacco product (ATP) use from Baseline to Week 4. Similarly, to address secondary aims related to biomarkers of nicotine exposure, 2 x 2 mixed models tested the effects of VLNC vs. NNC cigarettes on change in biomarkers of nicotine exposure (i.e., total nicotine equivalents [TNEs] and cotinine), as well as average number study cigarettes smoked per day relative to average number of usual brand cigarettes smoked per day. In all models, Group (VLNC = 1; NNC = 0) was a between-subjects predictor, and Time (Baseline vs. Week 4) was the repeated measure. Subject was treated as a random effect to account for subject-level differences in baseline outcome levels. The focal tests evaluated the difference in change from Baseline to Week 4 (i.e., Time) in the VLNC vs. NNC condition (i.e., Group), which is a cross-level interactive effect of Time and Group. A *p*-value < 0.05 was interpreted as meeting statistical significance criteria. For all estimation

parameters, we report effect estimates, standard errors, and 95% confidence intervals in addition to p values.

Consistent with the original statistical analysis plan, demographics and baseline data on participant tobacco use history and individual characteristics were summarized using univariate descriptive statistics (e.g., means, standard deviations, frequencies). Data visualization and formal statistical evaluation of means, standard deviations, skewness, and kurtosis, assessed the distributional characteristics of each outcome. Where the assumptions of models implementing a normal (Gaussian) outcome distribution were not met, the statistical approach was revised accordingly. The following analytic procedures were required to meet model assumptions and account for skewed outcome distributions and low frequency events for certain outcomes.

1. Average cigarettes per day was positively skewed, with a non-normal residual distribution in a mixed model analysis specifying a normal (Gaussian) outcome distribution. Therefore, this outcome was recoded to integers and modeled as a count with a negative binomial distribution and log link.

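### Randomisation is stratified on four factors that no SAP model includes, so inference is conservative to the extent that those factors predict change

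*Protocol*

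**What the plan says.** Protocol section 6.e gives the reason for stratifying: "We will stratify on the following four variables to optimally balance conditions on factors that might influence responses to study cigarettes". It lists gender and three past-month measures. Cigarettes per day is split as "CPD; < 8 cigarettes vs. > 8 cigarettes". The two ATP measures are given as "frequency of past-month alternative combustible tobacco product use (< 10 days vs. > 10 days" and "frequency of past-month non-combustible tobacco product use (< 10 days vs. > 10 days".

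The SAP, under *Analyses to address project aims*, sets the model terms: "In all models, Group (VLNC = 1; NNC = 0) was a between-subjects predictor, and Time (Baseline vs. Week 4) was the repeated measure". It adds: "Subject was treated as a random effect to account for subject-level differences in baseline outcome levels". The focal test is the Group × Time interaction. The SAP names no stratification factor in any model, plans no sensitivity analysis with them, and gives no reason for leaving them out. Its *Overview and justification* explains the choice of the mixed model in other terms, among them "to reduce bias stemming from (1) pre-randomization group differences in baseline outcome levels".

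**The concern.** The sponsor chose these four factors because they may affect response to the study cigarettes, which here means change from Baseline to Week 4. Stratified allocation makes the arms more alike on them than chance would. If the factors predict change, the treatment estimate therefore varies less from trial to trial than a model without them assumes. The model then reports a standard error that is too large.

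At stake is precision. The SAP states planned power of .74 for the smaller of its two effect sizes at 120 participants, and says that enrolment then fell short of that number. The factors were collected in order to randomise, so using them needs no new data.

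**Working it through.** **Inputs**
- Four two-level factors: Protocol 6.e.
- Fixed terms Group, Time and Group × Time, with a subject effect: SAP, *Analyses to address project aims*.
- Alpha 0.05: same section. Two-sided is assumed, because 95% intervals are reported.
- 120 participants, 60 per arm, power .74 at an estimate of .15 and .96 at .20: SAP, *Missing data and sample size considerations*. The number actually enrolled is not given.
- Share of the variance in change explained by the factors (R²): not in the documents. Varied from 0 to 0.30 as an assumption.
- Block size and full crossing of the factors: not stated. Blocks of 2 and crossed strata are assumed in the simulation.

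**1. The plan's power figures.** They cannot be rebuilt, because no SD or within-person correlation is given. With SD 1 and 60 per arm, power is .127 at .15 and .194 at .20. Working backwards, .74 at .15 implies a standard error of 0.15 / (1.960 + 0.643) = 0.0576. That predicts power of .935 at .20, where the SAP states .96. Nothing below rests on these figures except the power columns in step 3, which use .74 as an anchor.

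**2. Strata.** Fully crossed, 2⁴ = 16 cells. At 120 participants that is 120/16 = 7.5 per cell and 60/16 = 3.75 per arm within a cell, and fewer at the reduced enrolment. If the factors are modelled, they should therefore enter singly and not as 16 cells.

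**3. Closed form, continuous outcome.** With complete Gaussian data the Group × Time estimate is the difference between arms in mean change. If stratification balances the factors, the true variance of the estimate is (1 − R²) times what the unadjusted model reports. With total variance held fixed and ncp = 1.960 + 0.643 = 2.603:
- type I error = 2 × [1 − Φ(1.96/√(1 − R²))]
- interval width ratio = 1/√(1 − R²)
- unadjusted power = Φ((ncp − 1.96)/√(1 − R²))
- adjusted power = Φ(ncp/√(1 − R²) − 1.96)

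| R² (assumed) | Type I error, unadjusted | Width ratio | Power, unadjusted | Power, factor × Time |
|---|---|---|---|---|
| 0 | 0.050 | 1.00 | .740 | .740 |
| 0.05 | 0.044 | 1.03 | .745 | .761 |
| 0.10 | 0.039 | 1.05 | .751 | .784 |
| 0.20 | 0.028 | 1.12 | .764 | .829 |
| 0.30 | 0.019 | 1.20 | .779 | .875 |

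**4. Simulation check.** 120 participants, 16 strata, 4000 runs per setting, continuous outcome. At R² of about 0, 0.10, 0.20 and 0.30, type I error without the factors was .049, .041, .029 and .025. With factor × Time terms it was .046, .052, .044 and .048. This agrees with step 3 except at R² = 0.30, where the loss is somewhat smaller than the closed form gives.

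**5. Which terms matter.** In one simulated complete Gaussian data set, the Group × Time estimate was −0.7951 (SE 0.1771) without the factors and exactly the same with their main effects added. Main effects shift a person's level at both times and cancel in the change. Only the interactions with Time bear on the focal test.

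**6. What the models already carry.** The Baseline row and the subject effect hold the baseline week of the same outcome. That is related to past-month cigarettes per day or ATP use in the corresponding models, but it is not the stratum. Gender is in no model. The total nicotine equivalents and cotinine models contain none of the four factors.

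**7. Cut-points.** Strictly below 8 or above 8, and strictly below 10 or above 10, leave a value of exactly 8 or exactly 10 in neither level. This occurs on three of the four factors.

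**The case against.** The strongest reply is that balance is produced at allocation and protects the comparison whatever the model contains. That is correct. A reader might infer that the design's balance is wasted, or that the treatment estimate is biased. The documents support neither: leaving the factors out errs in the conservative direction, and has no effect if they do not predict change. Nor can one argue firmly that sparse cells leave imbalance uncorrected. The protocol states neither block size nor full crossing, and in the simulation the unadjusted test stayed conservative, which means that balance was largely achieved.

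The second reply is that the figures are Gaussian, while cigarettes per day is modelled as negative binomial and ATP use as binary. This stands. The table applies to the study-cigarette and biomarker outcomes, and the effect on the two primary outcomes has not been sized.

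The third is that the subject effect already deals with baseline differences. This stands only in part: a subject intercept absorbs differences in level, not differences in change.

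The fourth is that the cut-point gap may be an equals sign lost in printing. That is possible, although the protocol's exclusion criteria do print a greater-or-equal sign. The randomisation schedule would settle it.

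**Conclusion.** The SAP omits all four stratification factors from every model without explanation. The consequence is a loss of precision and a conservative test, not bias. For continuous outcomes with R² of 0, 0.10 or 0.20, the table gives type I error from 0.050 down to 0.028 and intervals up to 1.12 times too wide. These results assume complete Gaussian data, effective balance from stratification, and an R² that the documents do not supply. At R² = 0 there is no cost.

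The cut-point gap is a separate matter of definition and does not add to the precision loss. A reader might want to count the participants affected, but the documents give no distribution of past-month use from which to do so.

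**What to change.** Within the existing mixed models, add the four factors singly, each with its interaction with Time. The SAP is dated 9/1/23 and written in the past tense, so these should be reported as labelled stratification-adjusted analyses beside the stated models, not in place of them. Staying within the mixed model also respects the SAP's stated reasons for preferring it to ANCOVA. In the sparse binary ATP models, include only the factors that allow convergence; the SAP already reports that the combustible ATP model did not converge.

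Code the factors from the strata as implemented in the randomisation schedule, and state which level takes exactly 8 cigarettes and exactly 10 days.

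The cost is SAP wording and one further model run per outcome on data already collected. Each model gains up to eight terms (four main effects and four interactions), which uses a few degrees of freedom and may prevent convergence where events are few.
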